**Table 7 MFIQ DBT Analysis Visit Windows**

Analysis Visit	Study Day Analysis Visit Window	Target Day
Week 1	2 to 10	7
Week 2	11 to 17	14
Week 3	18 to 24	21
Week 4	25 to 31	28
Week 5	32 to 38	35
Week 6	39 to 45	42
Week 7	46 to 52	49
Week 8	53 to 59	56
Week 9	60 to 66	63
Week 10	67 to 73	70
Week 11	74 to 80	77
Week 12	81 to 98	84
Extension @	≥99	

@ Denotes an extended visit in the analysis period

Study days are used to define analysis visit windows in all analysis periods except follow-up safety. Follow-up days are used to define analysis visit windows in the follow-up safety analysis period.

## 8 CONTENTS OF REPORTS

See Section 1.2 for the timing of database locks and reports.

### 8.1 PCD Final CSR

The following TLFs are produced for the PCD Final CSR, which focuses on efficacy, safety, and outcomes research endpoints during the DBT Phase:

- Section 6.2 Study Population: all tables and listings
- Section 6.3 Efficacy: all tables and listings
- Section 6.3 Safety:
  - All listings, including safety narrative subject identifiers
  - On-DBT and post-DBT pre-OL rimegepant safety analysis periods: all tables and figures
  - On-OL rimegepant safety analysis period: tables of AE overview, AEs by worst intensity, AEs related to study drug by worst intensity, SAEs, AEs leading to study drug discontinuation, worst laboratory test abnormalities, and LFT elevations.

- Follow-up safety analysis period: tables of AE overview, AEs by worst intensity, and SAEs.
- Section 6.4 Outcomes Research: listing; tables of endpoints during the DBT Phase.

Tables of safety and outcomes research endpoints over time display results only during pretreatment and the DBT Phase.

## 8.2 LSLV Final CSR

All TLFs described in this SAP are produced for the LSLV Final CSR.

# 9 APPENDICES

## 9.1 Relevant Protocol Deviations

Relevant eligibility protocol deviations include the following categories:

- Previously treated with study drug in another multiple-dose BHV3000 study. Defined as subjects with (1) previous BHV3000 study subject identifiers from studies BHV3000-201/305/404/405/406 from the Demographics/Informed Consent CRF, and (2) who took  $\geq 1$  dose of study drug (e.g., rimegepant or placebo) in a multiple-dose study.
- Randomized or treated with study drug under  $>1$  subject identifier. These are identified from the Microsoft Excel file of protocol deviations extracted from clinical trial management system (CTMS) by Sponsor Clinical Operations.
- Migraine history issue, defined as any of the following subcategories:
  - $\leq 3$  or  $\geq 15$  migraine days per month of any pain intensity in the 3 months prior to screening
  - $\geq 15$  headache days per month in the 3 months prior to screening
  - $\geq 7$  nonmigraine headache days per month in the 3 months prior to screening, if originally consented to Protocol Version 4 or higher. Defined as {number of headache days per month in the 3 months prior to screening} – {number of migraine days per month of any pain intensity in the 3 months prior to screening}.

These are based on the Migraine History CRF.

- Finding out of range during pretreatment, defined any as any of the following subcategories:
  - Females with a positive pregnancy test (see Section 6.4.2)
  - Estimated glomerular filtration rate (eGFR) according to the re-expressed abbreviated (4-variable) Modification of Diet in Renal Disease (MDRD) Study equation  $\leq 40$  mL/min/1.73m^2, if originally consented to Protocol Version 4 or lower \*
  - eGFR according to the re-expressed abbreviated (4-variable) MDRD Study equation  $< 30$  mL/min/1.73m^2, if originally consented to Protocol Version 5 or higher \*
  - BMI  $\geq 33$  kg/m^2, if originally consented to Protocol Version 3 or lower \*

- BMI  $\geq 35$  kg/m^2, if originally consented to Protocol Version 4 or higher \*
- C-SSRS suicidal ideation with active intent or plan to act, or suicidal behavior present. Defined as having a “yes” response to any of the following C-SSRS questions during pretreatment:
  - Suicidal ideation question 4 (active suicidal ideation with some intent to act, without specific) or 5 (active suicidal ideation with specific plan and intent)
  - Suicidal behavior question 1 (actual attempt), 3 (interrupted attempt), 4 (aborted attempt), 5 (preparatory acts or behavior), or 6 (suicidal behavior).

Responses to lifetime questions at the Screening Visit are excluded from analyses.

For the subcategories marked with “\*”, all nonmissing values during the pretreatment analysis period must meet the deviation criteria in order to be considered a deviation.

- Nonstudy medication CRF data issue with ROM medication categories with previous inadequate response, defined as any of the following subcategories:
  - Number of ROM medication categories with previous inadequate response due to lack of efficacy or prior intolerance within 10 years of the Screening Visit  $\leq 1$  or missing
  - Number of ROM medication categories  $\leq 1$  or missing
  - Number of ROM medication categories  $\geq 5$

Medication categories based on nonstudy medication CRF data are defined in Section 9.4.2.

- Efficacy data issue during the first 28 days of the OP, defined as any of the following subcategories:
  - $\leq 3$  or missing migraine days
  - $\geq 15$  headache days
  - $\geq 7$  nonmigraine headache days, if originally consented to Protocol Version 4 or higher. A nonmigraine headache day is defined as a headache day that is not a migraine day.
  - $\leq 23$  days of eDiary efficacy data (see Sections 6.2.6.2 and 9.2.2). Subjects without any eDiary efficacy data are considered to have 0 days of eDiary efficacy data.

These are assessed during the 28-day OP analysis period (see Section 7.2). Migraine days and headache days are absolute, not prorated to 28 days per month (see Sections 9.2.5 and 9.2.6), and of total pain intensity.

Relevant subject management protocol deviations include the following categories:

- Randomization stratum discrepancies between the RTSM system and actual data, defined as any of the following subcategories:
  - Number of total migraine days during the first 28 days of the OP discrepant between the RTSM system and eDiary data. This is defined as any of the following subcategories:
    - RTSM value of “4 to 7” and eDiary value  $\leq 3$ ,  $\geq 8$ , or missing

- RTSM value of “8 to 14” and eDiary value  $\leq 7$ ,  $\geq 15$ , or missing.
- Number of ROM medication categories with previous inadequate response discrepant between the RTSM system and nonstudy medication CRF data. ROM medication categories based on nonstudy medication CRF data are defined in Section 9.4.2. This is defined as any of the following subcategories:
  - RTSM value of “2” and CRF value  $\leq 1$ ,  $\geq 3$ , or missing
  - RTSM value of “3 to 4” and CRF value  $\leq 2$ ,  $\geq 5$ , or missing.

See Section 6.2.5.1.

- DB study drug dosing noncompliance, defined as any of the following subcategories (see Sections 6.2.6.2 and 9.5):
  - DB study drug taken but not randomized
  - DB tablet count compliance  $< 80\%$  from study drug start to later of last scheduled DBT Phase visit or DB study drug end/OL rimegepant start
  - $> 1$  DB tablet taken on any 1 day
  - Consecutive DB study drug dosing days
  - Incorrect DB study drug taken.
- OL rimegepant dosing noncompliance, defined as any of the following subcategories (see Sections 6.2.6.2 and 9.5):
  - OL rimegepant tablet count compliance  $< 80\%$  from OL rimegepant start to later of last scheduled OLE Phase visit or OL rimegepant end
  - $> 1$  OL rimegepant tablet taken on any 1 day
  - Consecutive OL rimegepant dosing days
  - OL rimegepant start on or before DB study drug end
  - OL rimegepant taken but DB study drug never taken.
- eDiary usage compliance  $< 80\%$  from study drug start to later of last scheduled DBT Phase visit or DB study drug end/OL rimegepant start (see Section 6.2.6.2)
- Prohibited nonstudy medications taken on or after informed consent (or otherwise specified), defined as any of the following subcategories:
  - Atypical antipsychotic, divalproex, valproic acid, or valproate #
  - Ergotamine
  - Lamotrigine
  - Recognized prophylactic migraine medication taken up to 30 days before informed consent or afterward #. Recognized prophylactic migraine medication is defined as prophylactic migraine medication with preferred name containing any preferred name listed in the latest version of the sponsor-provided file Recognized Migraine Prevention

Medications.xlsx or equivalent. Prophylactic migraine medication is defined in Section 6.2.6.3.

- Narcotic (barbiturate or opioid) #
- Select moderate or strong cytochrome P450 3A4 (CYP3A4) inducer #
- Select strong CYP3A4 inhibitor #.

Note that nonstudy medications with route of “topical” or “intraocular” are excluded.

For the subcategories marked with “#”, preferred names are displayed alphabetically as additional subcategories. Medications taken up to  $X$  days before a reference date or afterward are defined as those with imputed medication start date or imputed end date  $\geq$  reference date –  $X$ . Refer to the Core SAP for additional details about prohibited nonstudy medications.

The RTSM randomization date is the reference date for “randomization”. If the RTSM randomization date is missing, then the study drug start date is used.

The protocol version to which subjects consented is determined from the Inclusion/Exclusion Criteria CRF.

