5.2. Inclusion Criteria

1) Target Population

Minimum 1 year documented history of migraines (with or without aura) consistent with a diagnosis according to the International Classification of Headache Disorders, 3rd Edition.¹²

Per self-report, with confirmation from Investigator / supporting medical record, subjects must have:

- a) Migraine attacks present for more than 1 year from the Screening Visit
- b) Age of onset prior to 50 years of age
- c) Migraine attacks lasting about 4–72 hours, if untreated
- d) 4 to 14 **migraine days** (based on ICHD-3 criteria), on average, across the 3 months prior to the Screening Visit (a month is defined as 28 days for the purpose of this protocol)
- e) 4 to 14 **migraine days** during the first 28-days of the Observation Phase

- f) Subjects must be able to distinguish migraine attacks from tension headaches
- g) Prior inadequate response, within 10 years of the Screening Visit, to agents across 2-4 categories of recognized, orally-administered migraine-preventive medications where at least one example of prior inadequate response is due to lack of efficacy or prior intolerance (not contraindication) (see Section [16.2 Appendix 2](#))
- h) **For Germany Only** please refer to [16.7.1](#)

2) Age and Reproductive Status

- a) Subjects ≥ 18 years-old
- b) Subject meets reproductive criteria. Refer to Section [16.6 Appendix 6](#) for reproductive criteria for female subjects (Section [16.6.2](#)).
- c) At the Baseline Visit, prior to dispensing investigational study drug, WOCBP must have a negative pregnancy test (minimum sensitivity 25 IU/L or equivalent units of HCG) before dosing with study drug.

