16.2. Appendix 2 – Recognized, Orally-Administered Migraine-Preventive Medications

Eligible subjects must have experienced, within 10 years of the Screening Visit, inadequate response (due to lack of efficacy or prior intolerance) to specified agents across 2-4 of the following categories of recognized, orally-administered migraine-preventive medications where at least one example of prior inadequate response is due to lack of efficacy or prior intolerance (not contraindication). Within Categories 1-7 this list of medications is specific and exclusive of other medications. Individuals with a history of inadequate response (due to a lack of efficacy, prior intolerance or contraindication) to agents across >4 of the following categories are to be excluded from this study.

- Category 1 Valproic acid: **specifically, divalproex sodium, sodium valproate**
- Category 2 Other anticonvulsant: **specifically, gabapentin, topiramate**
- Category 3 Beta blocker: **specifically, atenolol, bisoprolol, metoprolol, nadolol, propranolol, timolol**
- Category 4 Tricyclic antidepressant: **specifically, amitriptyline**
- Category 5 Serotonin-norepinephrine reuptake inhibitor (SNRI): **specifically, desvenlafaxine, venlafaxine**
- Category 6 Calcium-channel blocker: **specifically, flunarizine, verapamil**
- Category 7 Angiotensin blocker (angiotensin-converting enzyme [ACE] inhibitor, angiotensin II receptor blocker [ARB]): **specifically, candesartan, lisinopril**
- Category 8 Other: **locally-approved, or otherwise recognized standard of care, oral medications for the preventive treatment of migraine (e.g., methysergide, oxetrone, pizotifen).** If the subject has experienced inadequate response to a medication under this category, supporting documentation is required from the site noting the national or regional published guidelines as to why this medication had been included.

Inadequate Response is defined as meeting any of the following criteria:

- Lack of Efficacy:

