 - When prior treatment with a recognized, orally-administered, migraine-preventive medication has been previously interrupted because of an adverse event(s) that made continuation of the drug unacceptable, as determined by the Principal Investigator and documented within the medical/pharmacy record. If the Principal Investigator is not the treating physician and the medical/pharmacy record is not available for documentation purposes, the Principal Investigator can interview the treating physician to confirm the above information and document the interview with date and his/her signature. When the medical/pharmacy records are available indicating the subject's use of previous treatment with a recognized, orally-administered, migraine-preventive medication but there is no documentation on the lack of prior intolerance, an interview with the subject and documentation with date and time will suffice. This interview must capture a detailed description of the adverse effects from the prior prophylaxis treatment and the reasons the participant found it to be intolerable (e.g., severity, duration, impact on function, etc). Such evidence based on interview responses must be documented in sufficient detail to support the conclusion of intolerance to previous treatment.
- Contraindication:
 - When a recognized, orally-administered, migraine-preventive medication is contraindicated or otherwise considered inadvisable in accordance with locally recognized labelling, practice guidelines, and/or the current standard of care, as determined by the Principal Investigator with rationale documented within the medical record. If the Principal Investigator is not the treating physician and the medical record is not available for documentation purposes, the Principal Investigator can interview the treating physician to confirm the above information and document the interview with date and his/her signature. When the medical records or other objective evidence on screening are available indicating the subject's use of previous treatment with a recognized, orally-administered, migraine-preventive medication but there is insufficient documentation on the contraindication, a supplemental interview with the subject and documentation with date and time will suffice.

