#### **9.4.2 Number of ROM Medication Categories With Previous Inadequate Response**

The number of ROM medication categories with previous inadequate response is calculated as the sum across categories in which there is  $\geq 1$  medication with previous inadequate response due to (1) lack of efficacy within 10 years of the Screening Visit, (2) prior intolerance within 10 years of the Screening Visit, or (3) contraindication.

Analyses are based on medications in the migraine-preventive medication category of “recognized orally-administered migraine-preventive medication” from the Previous Experience With or Documented Contraindication to Prophylactic Migraine Medications CRF (see Section 9.4.1).

Medications with previous inadequate response due to lack of efficacy within 10 years of the Screening Visit are those that meet both of the following criteria:

- Inadequate response reason of “lack of efficacy”
- Screening visit date – 3651 days  $\leq$  nonstudy medication imputed start date or imputed end date  $\leq$  screening visit date – 1 day (see Section 7.1).

Medications with previous inadequate response due to prior intolerance within 10 years of the Screening Visit are those that meet both of the following criteria:

- Inadequate response reason of “prior intolerance”
- Screening visit date – 3651 days  $\leq$  nonstudy medication imputed start date or imputed end date  $\leq$  screening visit date – 1 day (see Section 7.1).

Medications with previous inadequate response due to contraindication are those with either (1) inadequate response reason of “contraindication” or (2) nonmissing contraindication reason.

- Medications with previous inadequate response due to contraindication due to hypersensitivity are those with contraindication reason of “hypersensitivity”.
- Medications with previous inadequate response due to contraindication due to other reason are those with contraindication reason of “other”.

- Medications with previous inadequate response due to contraindication reason not reported are those with both (1) inadequate response reason of “contraindication” and (2) missing contraindication reason.

If the number of ROM medication categories with previous inadequate response is NOT  $\geq 1$ , then the following apply:

- The number is set to 0 if either of the following criteria is met:

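### SAP 9.1 reports as eligibility deviations some subjects whom inclusion 1g admits: those with one efficacy or intolerance failure category plus one to three contraindication-only categories

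*SAP*

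**What the plan says.** Inclusion 1g (Protocol 5.2) has two parts. The first sets the total: "Prior inadequate response, within 10 years of the Screening Visit, to agents across 2-4 categories of recognized, orally-administered migraine-preventive medications". The second sets a minimum within that total: "where at least one example of prior inadequate response is due to lack of efficacy or prior intolerance (not contraindication". SAP 1.1 repeats the minimum of one.

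Protocol Appendix 2 (16.2) explains the criterion. Its opening sentence speaks of "inadequate response (due to lack of efficacy or prior intolerance) to specified agents across 2-4 of the following categories", with contraindication left out of the parenthesis, and then ends with the same minimum-of-one clause as 1g. Further down it states that "Inadequate Response is defined as meeting any of the following criteria", and the third of those criteria is that a medication "is contraindicated or otherwise considered inadvisable in accordance with locally recognized labelling, practice guidelines, and/or the current standard of care".

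The rest of the plan counts contraindication in the total. Exclusion 1e (Protocol 5.3) does so for the upper limit of four categories. The stratification text does so in Protocol 4.3.2.1, 5.1, 7.2.1 and 7.3 and in SAP 2.1. So does SAP 9.4.2: "The number of ROM medication categories with previous inadequate response is calculated as the sum across categories" with at least one medication that failed on efficacy, failed on tolerability or was contraindicated.

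SAP 9.1 opens its first list with "Relevant eligibility protocol deviations include the following categories". Under that list, one category has three ROM subcategories:

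- the "Number of ROM medication categories with previous inadequate response due to lack of efficacy or prior intolerance within 10 years of the Screening Visit" is one or less, or missing;
- the total number of ROM categories is one or less, or missing;
- the total is five or more.

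SAP 6.2.4.1 tabulates these deviations by treatment group and by type (eligibility or subject management) for the full analysis set, and adds a by-subject listing.

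**The concern.** The minimum-of-one clause in 1g does some work only if contraindication can supply the remaining categories. The first ROM subcategory in SAP 9.1 in effect requires two failure categories. A subject with one failure and one contraindication meets 1g but fails that check.

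The SAP then treats the same subject in two ways. SAP 9.4.2 gives a total of 2, and the cross-table in SAP 6.2.5.1 records agreement with a randomisation stratum of 2. SAP 9.1 reports an eligibility deviation.

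At stake is the accuracy of the reported eligibility deviations on the characteristic that defines this trial's population. If 1g governs, the study report would overstate them.

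**Working it through.** The plan gives no figure on this point to reproduce, so the check sets the rules side by side over every possible case.

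**Definitions**

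- E = number of ROM categories with lack of efficacy or prior intolerance within 10 years of screening.
- C = number of ROM categories with contraindication only.
- T = E + C, the total defined in SAP 9.4.2.

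**Rules**

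- Inclusion 1g, with exclusion 1e as upper limit: eligible if 2 ≤ T ≤ 4 and E ≥ 1.
- SAP 9.1 as written: flagged if E ≤ 1, or T ≤ 1, or T ≥ 5.
- Opening parenthesis of Appendix 2 taken alone: eligible if 2 ≤ E ≤ 4 and T ≤ 4.

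There are 21 pairs (E, C) with T from 0 to 5. Totals above 5 behave like 5: ineligible and flagged. Missing counts are flagged throughout and are not enumerated.

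| E | C | T | Pairs | Inclusion 1g | SAP 9.1 |
|---|---|---|---|---|---|
| 0 | 0 to 5 | 0 to 5 | 6 | ineligible | flagged |
| 1 | 0 | 1 | 1 | ineligible | flagged |
| **1** | **1, 2, 3** | **2, 3, 4** | **3** | **eligible** | **flagged** |
| 1 | 4 | 5 | 1 | ineligible | flagged |
| 2 | 0, 1, 2 | 2, 3, 4 | 3 | eligible | not flagged |
| 2 | 3 | 5 | 1 | ineligible | flagged |
| 3 | 0, 1 | 3, 4 | 2 | eligible | not flagged |
| 3 | 2 | 5 | 1 | ineligible | flagged |
| 4 | 0 | 4 | 1 | eligible | not flagged |
| 4 | 1 | 5 | 1 | ineligible | flagged |
| 5 | 0 | 5 | 1 | ineligible | flagged |

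**Results**

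- 1g admits 3 + 3 + 2 + 1 = 9 pairs and rejects 21 − 9 = 12.
- SAP 9.1 flags 12 + 3 = 15 pairs: all 12 ineligible ones, plus the three eligible ones in bold. No ineligible pair escapes.
- The Appendix 2 parenthesis taken alone admits 3 + 2 + 1 = 6 pairs. It differs from 1g in the same three pairs and nowhere else.
- With the first subcategory changed to E = 0 or missing, and the two checks on T kept, SAP 9.1 flags 6 + 6 = 12 pairs. These are exactly the 12 that 1g rejects.

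**Where the flag is used.** SAP 6.2.4.1 puts it in one table and one listing. The full, DBT efficacy and migraine analysis sets in SAP 4.1 depend on randomisation, dosing and eDiary days. The strata in SAP 6.2.5.1 use T. The power statement in SAP 5 uses 280 per group, a 1.0-day difference and an SD of 3.6 days. None of these involves the flag.

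**The case against.** The strongest reply is that this is a reporting detail and that other outputs carry the right information. SAP 6.2.4.1 shows every deviation subcategory, so the two checks on the total stay readable on their own lines. SAP 6.2.5.1 tabulates the number of ROM categories, SAP 6.2.5.4 separates failures by reason, and SAP 6.2.4.2 lists major deviations from an independent source. All of that stands and limits the harm. It does not make the flag correct.

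A second reply is that SAP 9.1 labels the item a CRF data issue. It does, but the item sits in the eligibility list and is tabulated under that type.

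A third is that the threshold may be deliberate. The SAP revision history records that Version 4 modified these subcategories, and the threshold fits the opening parenthesis of Appendix 2. Intent cannot be excluded, but 1g, SAP 1.1 and SAP 9.1 would still disagree. Nor does the item carry a consent-version condition, as the neighbouring eGFR, BMI and nonmigraine-headache items do.

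A reader might also infer that Appendix 2 sets a different entry rule, so that sites would enrol different populations. The text does not support that. The opening sentence itself ends with the minimum-of-one clause, which would be redundant under the stricter reading. Appendix 2 then counts contraindication both in its definition and towards the limit of four. Read whole, it agrees with 1g; the parenthesis is incomplete.

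**Conclusion.** The mismatch holds, within narrow limits. If 1g governs, SAP 9.1 would report as eligibility deviations those subjects with exactly one efficacy or intolerance category and one to three contraindication-only categories. These are three of the 21 combinations, and the error runs in one direction only.

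Three stronger inferences are not supported:

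- **Every subject with a single failure category is wrongly flagged.** With no contraindication category, or with four, the subject is ineligible under 1g and the flag is right.
- **The efficacy results are affected.** No analysis set, stratum, estimate or power figure depends on the flag.
- **The number of false deviations can be estimated.** The documents do not say how many subjects qualify through one failure plus contraindications. Each percentage point of the planned 600 would be 6 subjects (0.01 × 600), but any chosen percentage would be an assumption.

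The conclusion rests on reading 1g as letting contraindication supply the other categories. Exclusion 1e, the stratification text, SAP 9.4.2 and the Appendix 2 definition all support that reading.

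**What to change.** Reconcile inclusion 1g, Protocol Appendix 2 and SAP 9.1.

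- **If 1g stands as written:** change the first ROM subcategory in SAP 9.1 from one or less, or missing, to zero or missing. Keep the checks on the total (one or less; five or more), which catch the remaining ineligible cases. Add contraindication to the opening parenthesis of Appendix 2 so that it matches the rest of that appendix and 1g.
- **If the sponsor intends at least two failure categories:** the SAP threshold can stay, but 1g, its repeats (including SAP 1.1) and the stratification text must be reconciled to that rule.

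The first route costs one SAP threshold and one protocol clarification, with no new data and no change to any efficacy analysis. The second changes an entry criterion and is the larger amendment.
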